9.3. Statistical analyses

The SAP will include a more technical and detailed description of the statistical analyses. This section is a summary of the planned statistical analyses.

The analyses will be descriptive with the aim to characterize the safety/reactogenicity, and immunogenicity in each group.

Any deviation(s) or change(s) from the original statistical plan outlined in this Protocol will be described and justified in the final CSR.

9.3.1. Participants Disposition

The number of enrolled and administered (at least one dose, full dose course) participants, included in each group and in total, will be described.

9.3.2. Demography and Baseline Characteristics Analyses

Demographic characteristics (age at first study intervention administration in years, sex at birth, HSV-1 status, race, and ethnicity) will be summarized overall and by study intervention group using descriptive statistics:

- Frequency tables will be generated for categorical variables.
- Mean, SD, median, minimum and maximum will be provided for continuous data such as age, height, weight, and body mass index.

Withdrawal status will be summarized by group using descriptive statistics:

- The numbers of withdrawn participants will be tabulated according to the reason for withdrawal.
- The number of participants enrolled into the study as well as the number of participants excluded from the PPS will be tabulated.

9.3.3. Primary Endpoints/Estimands Analyses

The analysis of the primary reactogenicity and safety objective will be performed on the ES.

Statistical Analysis Methods

The percentage of participants reporting at least one solicited AE, at least one solicited administration site AE, and at least one solicited systemic AE during the 7-day follow-up period (i.e., Day 1-Day 7 post-each study intervention administration) will be tabulated for each group after each dose and overall.
 
The percentage of participants reporting each individual solicited administration site AE (any grade and Grade 3) and solicited systemic AE (any grade and Grade 3) during the 7-day follow-up period (i.e., Day 1-Day 7 post-each study intervention administration) will be tabulated for each group after each dose and overall.
 
For solicited AEs, percentages will be computed based on the total number of solicited symptoms screens completed.
 
For each group and for each hematology and biochemistry parameter:
 
• The percentage of participants having hematology and biochemistry results below or above the laboratory normal ranges will be tabulated by timepoint.• The summary of grading post-study intervention administration will be tabulated vs. baseline. Grades will be based on the FDA Guidance for Industry “Toxicity Grading Scale for Healthy Adults and Adolescent Volunteers Enrolled in Preventive Vaccine Clinical Trials”; see Section 10.2.2). The laboratory parameters not included on FDA Toxicity Grading Scale will not be graded. 
The percentage of participants with any unsolicited AEs during the 28-day follow-up period (i.e., Day 1-Day 28 post-each study intervention administration) with its exact 95% CI will be tabulated by group and by MedDRA PTs. Similar tabulation will be done for Grade 3 unsolicited AEs, for any causally related unsolicited AEs, for Grade 3 causally related unsolicited AEs and for unsolicited AEs resulting in a medically attended visit. The verbatim reports of unsolicited AEs will be reviewed by a qualified person and the signs and symptoms will be coded according to the MedDRA Dictionary for Adverse Reaction Terminology. Every verbatim term will be matched with the appropriate PT.
 
For unsolicited AEs, percentages will be computed based on the total number of exposed participants. Participants not reporting an AE will be considered as not having experienced any AE.
 
The percentage of participants with any AEs (solicited and unsolicited) resulting in a medically attended visit from Dose 1 up to 28 days post last dose administered (Day 57, or Day 29 if only one dose administered) will also be tabulated by MedDRA SOC and PT by group, after each dose and overall with exact 95% CI.
 
The percentage of participants with at least one report of SAE, with at least one report of causally related SAE, with at least one report of fatal SAE, and with at least one report of causally related fatal SAE classified by the MedDRA SOC and PTs reported from Dose 1 up to 28 days post last dose administered (Day 57, or Day 29 if only one dose administered) will be tabulated by group with exact 95% CI.
 
The percentage of participants with at least one newly diagnosed pIMD and at least one exacerbation of a pre-existing pIMD classified by the MedDRA SOC and PTs and reported from Dose 1 up to 28 days post last dose administered (Day 57, or Day 29 if only one dose administered) will be tabulated by group with exact 95% CI.
 
The percentage of participants using concomitant medication (any medication, any antipyretic, and any antipyretic taken prophylactically, respectively) during the 7-day follow-up period (i.e., Day 1-Day 7 post-each study intervention administration) and during the 28-day follow-up period (i.e., Day 1-Day 28 post-each study intervention administration) will be summarized by group after each dose and overall.

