3. OBJECTIVES, ENDPOINTS, AND ESTIMANDS

Table 3 Study objectives, endpoints and estimands

Objectives	Endpoints and estimands
Primary	
To evaluate the reactogenicity and safety of the HSVTI.	
 Percentage of participants reporting each solicited administration site event (redness, pain, and swelling) within 7 days (Day 1-Day 7) post-each dose. Percentage of participants reporting each solicited systemic event (fever, fatigue, headache, myalgia, arthralgia) within 7 days (Day 1-Day 7) post-each dose. Percentage of participants reporting unsolicited AEs within 28 days (Day 1-Day 28) post-each dose. Percentage of participants reporting MAEs from Dose 1 (Day 1) up to 28 days post-Dose 2 (Day 57). Percentage of participants reporting SAEs from Dose 1 (Day 1) up to 28 days post-Dose 2 (Day 57). Percentage of participants reporting newly diagnosed pIMDs from Dose 1 (Day 1) up to 28 days post-Dose 2 (Day 57). Percentage of participants reporting exacerbation of pre-existing pIMDs from Dose 1 (Day 1) up to 28 days post-Dose 2 (Day 57). Percentage of participants reporting any hematological and biochemical laboratory abnormalities at pre-study intervention administration (Day 1), post-Dose 1 (Day 8 and Day 29), and post-Dose 2 (Day 36 and Day 57).
Secondary	
To evaluate the humoral immune response induced by the HSVTI.	
 CCI antibody GMC and seropositivity rate (assessed by ELISA) at pre-study intervention administration (Day 1), 28 days post-Dose 1 (Day 29), and 28 days post-Dose 2 (Day 57).
To evaluate the cellular immune response induced by the HSVTI.	
 Geometric mean of CCI CD4+/CD8+ T-cells frequency expressing at least 2 activation markers (IFN-γ, TNF-α, IL-2, IL-13, IL-17, 4-1BB and/or CD40L) and including at least one cytokine (assessed by CFC) at pre-study intervention administration (Day 1), 28 days post-Dose 1 (Day 29) and 28 days post-Dose 2 (Day 57).
To evaluate the safety of the HSVTI up to the end of follow-up period.	
 Percentage of participants reporting MAEs from Dose 1 (Day 1) up to study end (Day 209). Percentage of participants reporting SAEs from Dose 1 (Day 1) up to study end (Day 209). Percentage of participants reporting newly diagnosed pIMDs from Dose 1 (Day 1) up to study end (Day 209). Percentage of participants reporting pre-existing pIMDs from Dose 1 (Day 1) up to study end (Day 209).

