## **4.8. Changes to Protocol- Defined Analyses**

N/A

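### Does using completed symptom screens as the denominator halve the overall solicited adverse event percentages?

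*Protocol*

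**What the plan says.** Protocol Section 3 (Table 3) defines the primary solicited endpoints by dose: "Percentage of participants reporting each solicited administration site event (redness, pain, and swelling) within 7 days (Day 1-Day 7) post-each dose", with a parallel endpoint for systemic events, "Percentage of participants reporting each solicited systemic event", over the same window. SAP Section 1.1 repeats both.

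Protocol Section 9.3.3 sets out the tabulations. The analysis set is the Exposed Set: "The analysis of the primary reactogenicity and safety objective will be performed on the ES". The measure is a participant percentage ("The percentage of participants reporting at least one solicited AE, at least one solicited administration site AE", and so on), and it "will be tabulated for each group after each dose and overall". The denominator follows: "For solicited AEs, percentages will be computed based on the total number of solicited symptoms screens completed". For unsolicited events the section uses another one: "For unsolicited AEs, percentages will be computed based on the total number of exposed participants". It adds that anyone who reports no event is taken to have had none.

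In the SAP, Section 4.6 refers to Section 4.2 for the main safety analyses. Section 4.2 is blacked out in the public copy. The contents page also lists a subsection on daily recording of solicited events (6.2.2.5), which falls in another blacked-out stretch. Section 6.2.3.8, which is readable, summarises each subject by maximal severity for each event and each dose. Section 4.8, "Changes to Protocol- Defined Analyses", is marked not applicable.

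**The concern.** The numerator is participants and the stated denominator is screens. After one dose the two units agree. Across two doses they need not: diary cards are handed out at both dosing visits (Protocol Table 1), so a fully dosed participant would be expected to contribute two solicited records.

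If the overall row divided participants by all screens, it would be roughly half the true percentage of participants affected, and with complete diaries it could never exceed 50%. If the numerator also counted screens, the row would become a percentage of doses under a participant label. Reactogenicity belongs to the primary objective, so an understated overall figure for either formulation would matter to anyone reading only that row.

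**Working it through.** **Inputs.** Group sizes of about 20, 20 and 10, with two doses each (Protocol Section 4.1). Percentage of participants as the measure, and screens as the stated denominator (Section 9.3.3). Clopper-Pearson as the general interval method for proportions (SAP Section 4.1.1). Assumption: one solicited screen per participant per dose; the documents give no number. The documents state no expected solicited percentage, so there is no figure of the plan's own to reproduce.

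**Per-dose rows.** With one screen per dose, screens completed after Dose 1 equal participants with Dose 1 data, and the same holds for Dose 2. The ratio is x/n on either wording, so the defined primary endpoints do not move.

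**Overall row, three readings.** Let N be participants, U those with the event after either dose, x1 and x2 those with it after each dose, and k the number of missing Dose 2 screens.

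- A, each participant with any completed screen counted once: U/N
- B, participants over all screens: U/(2N − k)
- C, screens over screens: (x1 + x2)/(2N − k)

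A against B with k = 0 (exact 95% limits; the counts are illustrations):

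| N | U | Reading A | Reading B |
|---|---|---|---|
| 20 | 18 | 90.0% (68.3–98.8) | 18/40 = 45.0% (29.3–61.5) |
| 20 | 14 | 70.0% (45.7–88.1) | 14/40 = 35.0% (20.6–51.7) |
| 20 | 10 | 50.0% (27.2–72.8) | 10/40 = 25.0% (12.7–41.2) |
| 20 | 6 | 30.0% (11.9–54.3) | 6/40 = 15.0% (5.7–29.8) |
| 10 | 5 | 50.0% (18.7–81.3) | 5/20 = 25.0% (8.7–49.1) |

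The ratio of B to A is N/(2N − k). For N = 20 that is 20/40 = 0.500, 20/39 = 0.513, 20/38 = 0.526 and 20/36 = 0.556 for k = 0, 1, 2 and 4.

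Reading C gives the average per-dose rate. With 50% at each dose it shows 50%, while the true participant percentage lies between 50% and 100%, and is 1 − 0.5 × 0.5 = 75% if the doses are independent.

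So the arithmetic behind the worry is correct, but the halving and the 50% ceiling belong to B alone.

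**Which reading the text supports.**

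1. The measure is stated as a percentage of participants. B does not give one, and C gives a percentage of doses. Only A delivers the named quantity.
2. No sentence says that screens are summed over doses.
3. The unsolicited sentence takes everyone exposed and treats non-reporters as event-free. Beside it, the solicited sentence does a different job: it leaves out people who returned no solicited data. That contrast concerns who has data.
4. Section 9.3.3 also asks for per-dose and overall figures for medically attended events and concomitant medication, in both cases as percentages of participants.

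**Would a mistake show?** With complete diaries U ≤ x1 + x2, so B is at most the average of the two per-dose percentages. A correct overall percentage is at least the larger of them. When the doses differ, B or C therefore gives an overall figure below a per-dose row in the same table, which a table review should catch. If the two per-dose rates are equal this check can miss C, and it misses B only where no participant reacted to both doses.

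**Other uses.** The numerical holding rules in Protocol Section 8.2.3.1 are framed in participants, with cut-offs of 1/20 and 5/20, so this denominator does not enter them.

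**The case for a change.** The strongest case for a change is textual. The sentence says a total number of screens, while the section's other denominator sentence says participants, so the authors evidently had both units available. Two records per fully dosed participant is the expected case. The readable SAP text gives no across-dose denominator, and SAP Section 4.8 declares no departure from the protocol. Of the three readings, only the one not spelled out gives the stated measure, and one added sentence would settle the matter at no data cost.

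Part of this stands: the sentence is loose, and a reader of the public documents cannot confirm how the overall row will be computed. The rest carries less weight. Protocol Section 9.3 describes itself as a summary and leaves technical detail to the SAP, and the SAP places where a denominator rule would naturally sit are redacted. Section 4.8 does not help either way, because spelling out a denominator is detail and not a change of analysis.

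The related worry about confidence intervals, that two correlated screens would be treated as independent, has no anchor in the readable text. Section 9.3.3 attaches exact intervals to unsolicited events, medically attended events, serious events and immune-mediated diseases, and attaches none to the solicited rows. The SAP's general interval method does not make screens the binomial unit.

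**Conclusion.** No change to the plan is needed. The primary endpoints are per dose and unaffected, given one screen per dose. The overall row is a supplementary tabulation in a descriptive study with no hypothesis tests. Its denominator is imprecise, but the stated measure points to participants with at least one completed solicited screen after any dose, each counted once, and on that reading the error is zero.

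A factor of 0.500 to 0.556 (0 to 4 of 20 Dose 2 screens missing) would arise only if someone divided participants by both doses' screens, which no readable passage instructs. Writing the definition down would record what a competent analyst would do anyway. The conclusion rests on the one-screen-per-dose assumption and on not treating the redacted SAP text as absent. If that text did sum screens over doses, the point would need to be reopened.

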9.2. Analysis sets

Table 14 Analysis sets

Analysis set	Description
Screened set	All participants who were screened for eligibility
Enrolled set	All participants who entered the study (who were randomized or received study intervention or underwent a post-screening procedure)
Exposed Set (ES)	All participants who will receive at least 1 dose of the study intervention.
Per Protocol for immunogenicity set (PPS_Immuno)	All eligible participants who will receive all doses as per protocol, will have immunogenicity results post-dose, will comply with dosing/blood draw intervals, without intercurrent conditions that may interfere with immunogenicity and without prohibited concomitant medication/vaccination. The analysis will be done according to the study intervention that participants received at dose 1.
Per Protocol for CMI set (PPS_CMI)	All eligible participants who will receive all doses as per protocol, will have CMI results post-dose, will comply with dosing/blood draw intervals, without intercurrent conditions that may interfere with immunogenicity and without prohibited concomitant medication/vaccination. The analysis will be done according to the study intervention that participants received at dose 1.

CCI

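### By-dose rows for unsolicited and medically attended AEs need the recipients of that dose as denominator; on the all-exposed rule, a post-Dose 2 percentage is too low if anyone misses Dose 2

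*Protocol*

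**What the plan says.** The primary endpoint in Protocol Section 3, repeated in SAP 1.1, is "Percentage of participants reporting unsolicited AEs within 28 days (Day 1-Day 28) post-each dose".

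Protocol 9.3.3 sets the analysis population: "The analysis of the primary reactogenicity and safety objective will be performed on the ES". Table 14 in Protocol 9.2 defines that set as "All participants who will receive at least 1 dose of the study intervention". For the denominator, 9.3.3 states "For unsolicited AEs, percentages will be computed based on the total number of exposed participants", followed by "Participants not reporting an AE will be considered as not having experienced any AE".

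The layouts in 9.3.3 differ by event type:
- Unsolicited AEs: the percentage "with its exact 95% CI will be tabulated by group and by MedDRA PTs". By-dose rows are not mentioned.
- Solicited AEs: "will be tabulated for each group after each dose and overall", with completed symptom screens as the denominator.
- Medically attended AEs, solicited and unsolicited combined: "will also be tabulated by MedDRA SOC and PT by group, after each dose and overall with exact 95% CI". Section 9.3.4 repeats this layout up to Day 209, also on the Exposed Set.

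SAP 6.2.1 assigns each event to the most recent dose given before it started. SAP 4.6 refers the main safety analyses to Section 4.2, which cannot be read in the public copy. SAP 4.8 lists no changes to the protocol-defined analyses.

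**The concern.** A post-Dose 2 percentage should describe people who were given Dose 2. Under the stated rule, someone who stopped after Dose 1 remains in the denominator and is scored as having had no event after a dose they did not receive. Because SAP 6.2.1 ties events to the last dose given, nothing that happens to that person later can count as a Dose 2 event.

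The error runs in one direction, towards a more favourable Dose 2 safety profile. It need not be equal across groups. Protocol 7.1.1 withholds further doses for several safety reasons, including related SAEs, some related AEs, hypersensitivity, certain pIMDs and abnormal laboratory values. If these arise more often in one group, that group's Dose 2 percentage is diluted most, which affects both the comparison with placebo and the comparison of Dose 2 with Dose 1. SAP 4.1.1 does not replace participants who withdraw.

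**Working it through.** The documents give no expected AE rate and no expected number missing Dose 2, so there is no plan figure to reproduce.

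**Inputs**
- N = 20, 20 and 10 exposed (Protocol 4.1 and 6.3.3).
- d = number exposed who do not receive Dose 2. Assumed: 1, 2 or 4 in a group of 20; 1 or 2 in the group of 10.
- x = number with an event after Dose 2. Assumed: 4 in a group of 20; 2 in the group of 10.
- Intervals: 95% Clopper-Pearson (SAP 4.1.1).

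**Formulae**
- Percentage on all exposed: x/N.
- Percentage on Dose 2 recipients: x/(N-d).
- Ratio of the first to the second: (N-d)/N, whatever the value of x above zero.

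**Results**

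| N | d | Factor (N-d)/N | On all exposed (95% CI) | On Dose 2 recipients (95% CI) | Shortfall, points |
|---|---|---|---|---|---|
| 20 | 0 | 1.00 | 4/20 = 20.0% (5.7-43.7) | 4/20 = 20.0% (5.7-43.7) | 0 |
| 20 | 1 | 0.95 | 4/20 = 20.0% (5.7-43.7) | 4/19 = 21.1% (6.1-45.6) | 1.1 |
| 20 | 2 | 0.90 | 4/20 = 20.0% (5.7-43.7) | 4/18 = 22.2% (6.4-47.6) | 2.2 |
| 20 | 4 | 0.80 | 4/20 = 20.0% (5.7-43.7) | 4/16 = 25.0% (7.3-52.4) | 5.0 |
| 10 | 1 | 0.90 | 2/10 = 20.0% (2.5-55.6) | 2/9 = 22.2% (2.8-60.0) | 2.2 |
| 10 | 2 | 0.80 | 2/10 = 20.0% (2.5-55.6) | 2/8 = 25.0% (3.2-65.1) | 5.0 |

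The interval for 4/20 is 43.7 - 5.7 = 38.0 points wide, so a shortfall of 1.1 or 2.2 points is small beside it.

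The interval is affected even with no events: the upper limit is 16.8% on 20 but 18.5% on 18.

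**Uneven d.** Suppose an HSVTI group has x = 4 and d = 4, and placebo has x = 2 and d = 0. On all exposed, both read 20.0% (4/20 and 2/10). On Dose 2 recipients they read 25.0% (4/16) and 20.0% (2/10), so a 5.0-point difference disappears.

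**The case against.** The strongest reply is that the sentence on unsolicited AEs never promises by-dose rows, although the same section does so for solicited and medically attended AEs. Read literally, it may give one table pooling both 28-day windows, for which all exposed participants is a proper denominator. That stands, and it makes the point conditional for unsolicited AEs. But a pooled table alone would not report the endpoint as worded in Section 3, and the medically attended AE tables do have by-dose rows.

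For those tables the denominator is unspecified, not shown to be wrong. The all-exposed sentence covers unsolicited AEs only, the combined table mixes in solicited AEs, and the only pointer is the Exposed Set as analysis population. Section 9.3.3 also closes the window at Day 29 for one-dose participants, so the protocol foresees them.

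Protocol 9.3 calls itself a summary and leaves detail to the SAP. The redacted SAP 4.2 may hold a dose-specific denominator, and its absence cannot be asserted. Against that, such a rule would depart from an explicit protocol sentence, and SAP 4.8 records no departure.

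Dose 2 recipients are a selected group, since they did not stop after Dose 1. The two denominators answer different questions, and restricting to recipients does not give a fully randomised comparison. This is why the overall rows should stay on the Exposed Set. Missing Dose 2 is also not always a safety matter: unwillingness and pregnancy are among the other reasons.

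Finally, Protocol 9.3.1 and SAP 6.1.3 will show how many received each dose, so a reader could rescale an overall count. That softens the problem but leaves the tabulated percentages and intervals as they are.

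**Conclusion.** The point holds conditionally. Any post-Dose 2 percentage built on the stated rule is understated by (N-d)/N. This needs by-dose rows to be produced, exposed to mean the whole Exposed Set, and at least one participant to miss Dose 2. For one or two missed doses in a group of 20 the shortfall is 1.1 to 2.2 points at 20%, well inside the interval; at four it is 5.0 points. No hypothesis is tested, so no formal conclusion changes. What is affected is a descriptive safety percentage, always in the favourable direction.

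Three stronger readings are not supported:
- **That the Dose 2 results will certainly be diluted.** The readable text does not establish the conditions above, and SAP 4.2 may resolve the first two.
- **That the Day 36 and Day 57 laboratory tables share the fault.** These are tabulated by timepoint from measured values, and neither the all-exposed sentence nor the event-free rule is written for them.
- **That a study hold would leave half a group without Dose 2.** Protocol 5.5 allows the interval between doses to extend up to 90 days in that situation, and 8.2.3.1 provides for restart, so a hold need not forfeit Dose 2.

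**What to change.** In Protocol 9.3.3 and 9.3.4, state that by-dose rows for unsolicited and medically attended AEs use the participants who received that dose as the denominator, and that overall rows use the Exposed Set. Say at the same time whether unsolicited AEs will be tabulated by dose, so that the analysis matches the endpoint. Check that SAP 4.2 agrees; if it already uses dose recipients, align the protocol sentence with it.

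The cost is one sentence and a denominator flag in the table programs. The counts needed are already planned in SAP 6.1.3. No new data are required. By-dose percentages will be slightly higher wherever Dose 2 was missed and events followed it.
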